#### 9.19 Submission of trial data

Data will be entered by site research staff on trial-specific eCRFs, which will be provided by CTRU on a trial-specific database, access to which will be provided by the CTRU following sites authorisation to open to recruitment.

RDE/eCRFs must only be completed by personnel authorised to do so by the PI at site, as recorded on the trial-specific Authorised Personnel Log (APL). Login details will be provided for these personnel only and should not be shared with others.

Completed NCF test paper forms should be returned to the CTRU within 28 days of completion for quality control and scoring purposes. In addition, completed NCF forms used in practice sessions with colleagues as part of the training process must also be returned to CTRU as soon as possible for review (see **NCF Test Administration Guidelines**).

The electronic platform CNS Vital Signs, used for completion of the secondary NCF tests, automatically scores tests and produces a report, which will be sent directly to the CTRU.

## 9.20 Electronic Case Report Forms (eCRFs)

A number of eCRFs which require expedited reporting to the CTRU, should be entered within the time points specified below:

- A scanned copy of any consent forms must be sent to the CTRU via the in-house SFTS and the corresponding eCRF entered at the time of consent
- A paper Contact Details CRF should be sent to the CTRU via the SFTS immediately after randomisation
- SAR (serious adverse reaction) and RUSAE (related unexpected serious adverse events) eCRFs must be entered within 24 hours of the site becoming aware of the event. Please note: a paper SAR and RUSAE form will also be provided as a backup in the event any urgent reporting is required and the MACRO database cannot be accessed
- Protocol Violations eCRFs must be entered within 24 hours of the site team becoming aware of the event
- Notification of Pregnancy eCRFs must be entered within 24 hours of the site team becoming aware
- Any Notification of Death eCRFs must be entered within 7 days of the site team becoming aware
- Any Withdrawal Request eCRFS must be entered within 7 days of the date of withdrawal
- End of treatment eCRFs must be entered within 14 days of completion of PBT or photon RT

All other eCRFs must be completed within 28 days of the data collection time points detailed in Table 3 Assessment Schedule for both PBT and photon RT.

Only the participant's trial number, date of birth and initials will be added to the eCRFs – site staff are responsible for ensuring the data returned to CTRU does not contain any other personal identifiable data. The exception to this is any copies of the consent form, where the participant/caregiver/authorised investigator name and signature must not be obliterated.

Following receipt of any completed eCRFs, the CTRU will contact sites on a regular basis to resolve any missing or discrepant data.

# **10 Safety Reporting**

# 10.1 General definitions

# 10.1.1 Adverse Event (AE)

An adverse event (AE) is any untoward medical occurrence in a patient or clinical trial participant which does not necessarily have a causal relationship with the treatment. Non-serious AEs which have no causal relationship with trial treatment will not be recorded in this trial, but must still be recorded in the participant's medical notes

## 10.1.2 Adverse Reaction (AR)

Adverse reactions (ARs) are all untoward and unintended responses to a trial treatment.

This definition implies a reasonable possibility of a causal relationship which is supported by facts, evidence or arguments to suggest a causal relationship. This definition includes medication errors and uses outside what is foreseen in the protocol (i.e. if an AR occurs as a result of a medication error).

Trial treatment in APPROACH is defined as radiotherapy (photons or protons) **and** adjuvant chemotherapy.

## 10.1.3 Serious Adverse Event (SAE)

A Serious Adverse Event (SAE) is any untoward medical occurrence or effect that:

- Results in death.
- Is life-threatening\*.
- Requires inpatient hospitalisation or prolongation of existing hospitalisation.
- Results in persistent or significant disability or incapacity.
- Consists of a congenital anomaly or birth defect.
- Jeopardised the subject or required intervention to prevent one of the above.

\*The term life-threatening refers to an event in which the participant was at risk of death at the time of the event; it does not refer to an event which hypothetically might have caused death if it was more severe.

Medical judgement should be exercised in deciding whether an SAE is serious (see protocol section. These characteristics / consequences must be considered at the time of the event.

#### 10.1.4 Serious Adverse Reaction (SAR)

A Serious Adverse Reaction (SAR) is an SAE deemed to have been related to trial treatment. For the purposes of safety reporting trial treatment in APPROACH is defined as radiotherapy (photons or protons) and adjuvant chemotherapy. Safety monitoring of reactions to chemotherapy will be included and as such will be reported under the toxicity secondary objective (see section 13.5), however, there is no hypothesis of expected differences and no plan for formal comparisons. These events are collected for monitoring

purposes, and completeness of symptom reporting for this patient population across the course of the trial.

Medical and scientific judgement must be exercised in deciding whether an event is serious (see section 10.4 Responsibilities). These characteristics/consequences must be considered at the time of the event and do not refer to an event which hypothetically may have caused one of the above. Important SAE/SARs that are not immediately life-threatening or do not result in death or hospitalisation but may jeopardise the subject or may require intervention to prevent one or the other outcomes listed in the definition above, should also be considered serious.

# 10.1.5 Related Unexpected Serious Adverse Event (RUSAE)

A serious adverse reaction which is related and unexpected (termed Related Unexpected Serious Adverse Event, or RUSAE) will require expedited reporting (see section 9.20 Electronic Case Report Forms (eCRFs)) to enable reporting to the main Research Ethics Committee (REC) and Sponsor.

The Health Research Authority (HRA) defines the terms related and unexpected as:

- Related: that is, it resulted from administration of any research procedures.
- Unexpected: that is, the type of event that in the opinion of the investigator is not considered expected.

When determining whether an SAR is expected or not, please refer to Appendix B – Treatment toxicities for a list of expected radiotherapy related side effects and, for expected chemotherapy-related toxicities, additionally refer to the relevant version of the SMPC that is used locally.

# 10.2 Reporting requirements for ARs

Non-serious AEs which have no causal relationship with trial treatment will not be collected in this trial, but must still be recorded in the participant's medical notes.

Information about all ARs, whether volunteered by the participant, discovered by investigator questioning or detected through physical examination, laboratory test or other investigation will be collected and recorded on the relevant eCRF and will be evaluated for duration and intensity according to the current NCI-CTCAE, see Appendix A NCI-CTCAE.

Information on all radiotherapy related ARs will be collected weekly during PBT or photon RT and until the end of trial according to the assessment schedule illustrated in Table 3. All chemotherapy related ARs will be collected during chemotherapy up to 42 days after the last cycle received.

# 10.3 Recording and reporting SARs and RUSAEs

Examples of events which will be classed as expected ARs and SARs within this trial and therefore will not be reportable as RUSAEs are given in Appendix B Treatment Toxicities. This is not intended to be an exhaustive list, therefore when determining whether an SAR is expected or not, please always refer to the relevant SMPC that is used locally.

#### 10.3.2 Events classed as expected SARs

Examples of events that **will be** classed as expected SARs within this trial and therefore will not be reportable as RUSAEs unless the Investigator considers the severity to be unexpected are given in Appendix B Treatment Toxicities. In relation to chemotherapy treatment, the toxicities listed in Appendix B Treatment Toxicities are not intended to be an exhaustive list, therefore when determining whether an SAR is expected or not, please always refer to the relevant approved SMPC.

#### 10.3.3 Expected ARs and SARs related to chemotherapy

For a full list of expected side effects for lomustine, procarbazine or vincristine please see individual drug SMPCs, which can be found on the Electronic Medicines Compendium (http://medicines.org.uk). Please use the approved version of the SMPC when determining if toxicities are expected or not.

Most ARs related to chemotherapy are mild to moderate (CTCAE v5.0 Grade 1-2) and reversible, but severe and life-threatening reactions (Grade 3-4) can occur.

Potential ARs are listed in Appendix B Treatment Toxicities. These may occur with any degree of severity (i.e. mild to severe). Only episodes considered as serious, as per the description above (Section 10.1.3 Serious Adverse Event (SAE) and Reaction (SAR)) should be reported as SARs.

Toxicities and dose modifications should be managed according to local guidelines.

#### 10.3.4 Expected ARs and SARs related to radiotherapy

Potential ARs are listed in Appendix B Treatment Toxicities. These may occur with any degree of severity (i.e. mild to severe). Only episodes considered as serious, as per the description above (Section 10.1.3 Serious Adverse Event (SAE) and Reaction (SAR)) should be reported as SARs.

Toxicities related to radiotherapy should be managed according to local protocols. This may require increases in dexamethasone dose.

Toxicities related to chemotherapy should be managed according to local protocols.

#### 10.3.5 Reporting and recording requirements for SARs and RUSAEs

All ARs (any grade), are to be reported as per the AR reporting period in section 10.2 Reporting requirements for ARs.

All SARs and RUSAEs for all participants occurring during treatment must be recorded on the appropriate SAR or RUSAE eCRF within 24 hours of the trial site team becoming aware of the event, regardless of causality. Please note: a paper SAR and RUSAE form will also be provided as a back-up in the event any urgent reporting is required and the MACRO database cannot be accessed. Selected late toxicities occurring during follow-up must also be recorded and reported as above.

SARs and RUSAEs will be collected throughout trial treatment and up until the end of the trial according to the assessment schedule, this is defined as the active trial monitoring period.

For each SAR and RUSAE the following information will be collected:

- Full details in medical terms with a diagnosis, if possible
- Case description
- Event duration (start and end dates, if applicable)
- Seriousness criteria
- Outcome
- Action taken
- Whether the event would be considered expected or unexpected

Assessment of expectedness must be made by an authorised medically qualified person. If such a person is unavailable, initial reports without causality and expectedness assessment should be submitted to CTRU by a healthcare professional within 24 hours but must be followed up by medical assessment as soon as possible thereafter.

Please ensure that each event is reported separately and not combined on one SAR eCRF.

Any change of condition or other follow-up information should be entered within 24 hours of the research team becoming aware of the information. Events will be followed up until the event has resolved or a final outcome has been reached.

All SARs assigned by the PI or delegate (or following Chief Investigator review) as unexpected will be classified as a RUSAE and will be subject to expedited reporting to the Sponsor and REC by the CTRU on behalf of the Chief Investigator in accordance with current HRA guidance, CTRU Standard Operating Procedures (SOPs) and Sponsor requirements.

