#### 6.6 Essential documentation

The following documentation must be submitted by the site to the CTRU prior to site activation:

- All relevant institutional approvals (e.g., local NHS permission).
- A completed authorised personnel log that is initialled and dated by the PI (with all tasks and responsibilities delegated appropriately).
- Completed Site Contacts Form (with contact information for the PI, co-investigators, research/trial, pharmacy, radiography).
- A copy of the PI's current CV that is signed and dated.
- A copy of PI's current GCP training certificate.
- Signed PI declaration.
- RTTQA approval.
- A signed Clinical Trial Site Agreement (model Non-commercial Agreement for UK sites) between the Sponsor and the relevant institution.

- NCF Quality Assurance Log.
- Site Initiation Training Log.

Centres are asked wherever possible to make every effort to manage patients for trial purposes on one central site (usually the recruiting site), with the exception of SAR/RUSAEs experienced by participants undergoing PBT see section 10 Safety Reporting for definitions of SAR/RUSAEs). Paper back-up copies of these forms will be kept in the site file at the referral site where PBT was received instead of the recruiting site.

Sites must inform the CTRU of any additional sites involved in the patient pathway. Recruiting sites, which will be referring patients to a different site, for all or some of the trial activities, will not be activated until the relevant site involved is ready to be activated.

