## **10.4 Responsibilities**

## Principal Investigator (PI)

- 1. Checking for ARs when participants attend for treatment.
- 2. Using medical judgement in assigning seriousness and expectedness using the relevant SMPC used locally.
- Ensuring that all SARs, (including RUSAEs) are recorded and reported to the CTRU within 24 hours of becoming aware of the event and provide further follow-up information as soon as available. Ensuring that SARs (including RUSAEs) are chased with CTRU if a record of receipt is not received within 2 working days of initial reporting.
- 4. Ensuring that ARs are recorded and reported to the CTRU in line with the requirements of the protocol.

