#### Early and late toxicity

Summary statistics of safety data on ARs/SARs/RUSAEs experienced will be presented overall and by treatment arm for the acute and late toxicity period. The number and proportion of participants experiencing each CTCAE grade of acute and late toxicities will be summarised.

The long-term collection of clinician recorded toxicities will capture a level of symptom burden as a result of treatment. CTCAE grades of patients over time will be assessed to explore the time dependence of ARs in a population that can often experience chronic conditions. Additionally, this longitudinal data will be explored in relation to other endpoints over time e.g. HRQoL.

Safety monitoring of reactions to chemotherapy will be included and as such will be reported under the toxicity secondary objective, however, there is no hypothesis of expected differences and no plan for formal comparisons – this is being used to inform the safety of

the radiotherapy comparison. These events are collected for monitoring purposes, and completeness of symptom reporting for this patient population across the course of the trial.

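### Section 10.3.5 orders SARs and RUSAEs recorded whatever their causality, although relatedness is part of their definition and no relatedness item is listed or assigned

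*Protocol*

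**What the plan says.** Section 10.1.4 of the protocol gives the definition: "A Serious Adverse Reaction (SAR) is an SAE deemed to have been related to trial treatment". Trial treatment means radiotherapy, photon or proton, and adjuvant chemotherapy. Section 10.1.5 defines a RUSAE as a serious adverse reaction that is both related and unexpected.

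Section 10.3.5 says that SARs and RUSAEs occurring during treatment go on the corresponding eCRF "within 24 hours of the trial site team becoming aware of the event, regardless of causality". It then lists what is collected for each event: medical details, case description, duration, seriousness criteria, outcome, action taken, and "Whether the event would be considered expected or unexpected". Relatedness is not listed. The same section allows that, when no medically qualified assessor is available, "initial reports without causality and expectedness assessment should be submitted to CTRU by a healthcare professional within 24 hours", with medical assessment to follow.

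Section 10.4 describes the Principal Investigator's second duty as "Using medical judgement in assigning seriousness and expectedness using the relevant SMPC used locally". The Chief Investigator's second duty, which applies where local assessment could not be obtained, likewise names seriousness and expectedness only.

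On what is left out, Section 10.2 says: "Non-serious AEs which have no causal relationship with trial treatment will not be collected in this trial". On analysis, Section 13.5 says: "Summary statistics of safety data on ARs/SARs/RUSAEs experienced will be presented overall and by treatment arm", for the acute and late periods.

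**The concern.** An event that must be related in order to qualify cannot also be recorded irrespective of relatedness. A site following Section 10.1.4 would send related serious events only. A site following the last words of the Section 10.3.5 instruction would send every serious event. The number of participants counted as having a SAR would then depend on which sentence the site followed.

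Two things are at stake. The first does not depend on arm. Section 10.3.5 classifies every SAR assigned as unexpected as a RUSAE. An unrelated serious event may well be absent from Appendix B and the SmPC, so once it is on a SAR form it can be judged unexpected. It would then go to Chief Investigator review within 24 hours and to the REC and Sponsor within 1 working day (Section 10.4), although it is not a reaction at all.

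The second is the comparison by arm. During radiotherapy the PBT arm is looked after by clinicians at two PBT centres, who act as investigators for that period (Sections 3.1.2 and 7.1). The photon arm is looked after at the local centres, with 18-25 recruiting sites. Section 6.6 asks for single-site management "with the exception of SAR/RUSAEs experienced by participants undergoing PBT". If the two PBT centres shared one reading and the local centres mostly took the other, the open-label SAR summaries for that period would differ for a reason unrelated to toxicity.

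**Working it through.** No figure in the protocol underlies this point, so the check is mainly a comparison of text.

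**1. Can both sentences be satisfied?**
- Sections 10.1.4 and 10.1.5: the event must be related.
- Section 10.3.5: the event is recorded whatever its causality.
- Read literally, the second makes the first idle. Read through the definitions, the causality phrase has nothing to act on. A site has to choose.

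**2. Does another section settle it?** Sections 10.1.1 and 10.2 exclude unrelated events only if they are non-serious. Unrelated serious events are neither included nor excluded. Section 9.20 lists SAR and RUSAE eCRFs but no SAE eCRF. That leans towards related events only, without saying so.

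**3. Would the listed data allow a later correction?** Of the seven items in Section 10.3.5, none is relatedness. Neither of the two duties in Section 10.4 that assign medical judgement names it. Yet the sentence on initial reports presupposes a causality assessment. The protocol relies on an assessment that it neither lists nor assigns.

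**4. When does the responsible centre differ by arm?**

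| Period | Photon arm | PBT arm |
|---|---|---|
| During RT (about 6 weeks) | local centre | PBT centre |
| After RT, chemotherapy, follow-up | local centre | local centre |

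Section 11.2 runs the acute period from the start of RT to the assessment 3 months after its end. Taking 3 months as about 13 weeks, RT fills about 6/(6 + 13) = 32% of that window. The other two thirds or so, and the whole late period, have no arm-linked difference in responsible centre.

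**5. Illustration of size (all rates assumed).** Let r be the true risk of a related SAR, equal in both arms, and u the added proportion recorded in one arm only because its centres also send unrelated serious events. The arm size is 123 (Section 12.1). The false difference is (r + u) − r = u. The chance of a nominal two-sided p < 0.05 is approximately Φ[(u − 1.96·SE₀)/SE₁], where SE₀ = √(2·p̄(1 − p̄)/123), p̄ = r + u/2, and SE₁ = √([r(1 − r) + (r + u)(1 − r − u)]/123).

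For r = 5% and u = 5%: SE₀ = √(2 × 0.075 × 0.925/123) = 0.0336, SE₁ = √((0.0475 + 0.09)/123) = 0.0334, and Φ[(0.05 − 1.96 × 0.0336)/0.0334] = Φ(−0.47) ≈ 0.32.

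| r | u | Expected participants with a SAR | Chance of nominal p < 0.05 |
|---|---|---|---|
| 5% | 2% | 6.2 vs 8.6 | 10% |
| 5% | 5% | 6.2 vs 12.3 | 32% |
| 5% | 10% | 6.2 vs 18.5 | 75% |
| 10% | 2% | 12.3 vs 14.8 | 7% |
| 10% | 5% | 12.3 vs 18.5 | 22% |
| 10% | 10% | 12.3 vs 24.6 | 59% |

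This is the extreme case, in which all centres for one arm read the rule one way and all centres for the other arm read it the other way. A split among the local centres shrinks the difference. The last column only gives a sense of scale, because no test on SARs is planned.

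**The case against.** The strongest defence is that the instruction's subject is SARs and RUSAEs, which the definitions already limit to related events. Sections 9.20, 10.4, 11.2 and 13.5 all speak of SARs and never of all SAEs. The causality phrase follows a 24-hour clause, so it may only mean that a report should not wait for the causality assessment, in line with the later sentence on initial reports. This is a plausible account of the intent. It does not remove the conflict, because that later sentence covers only the case where no medically qualified person is available, and nothing says that the earlier phrase is limited in the same way.

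A reader might infer that the CTRU could never separate related from unrelated events. The documents do not support that. The eCRF is not shown and may hold a relatedness field. A case description is collected, incomplete reports must be followed up by medical assessment, and the CTRU verifies SARs centrally. What stands is that the protocol's own list and duties do not secure the information.

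A reader might also infer that the early-toxicity comparison is fully confounded with arm. That does not hold either. The responsible centre differs by arm only during RT, and all sites receive a common initiation (Section 6.5). Nothing shows that readings will split along arm lines. The SAR summaries are descriptive and secondary.

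**Conclusion.** The protocol is wrong as written on a limited point. Its definitions of SAR and RUSAE conflict with its recording instruction, no other section resolves the conflict, and relatedness is neither listed for collection nor named in the duties of those who judge the events. This leaves open which events are counted as SARs and which unexpected ones go forward for expedited reporting.

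A distortion of the by-arm comparison is possible for serious events arising during RT. It is conditional on the PBT centres reading the rule differently from the local centres, which the documents do not show. No size can be given without assumed rates. Under the assumed 2 to 10 extra percentage points and a complete split by arm, the false difference would be those same 2 to 10 points, and at the lower end it would hardly be noticeable. The primary endpoint of neurocognitive function is not touched. The case for correction rests on the contradiction itself and on how little it costs to remove, not on a demonstrated bias.

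**What to change.** Reconcile Sections 10.1.4, 10.1.5, 10.3.5 and 10.4 as follows.

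- **Section 10.3.5, instruction:** delete the causality phrase. If the intent was speed, replace it with a statement that initial reporting must not wait for the causality assessment.
- **Section 10.3.5, item list:** add relatedness to radiotherapy and relatedness to chemotherapy for each SAR and RUSAE.
- **Section 10.4:** name relatedness beside seriousness and expectedness in the second duty of both the Principal Investigator and the Chief Investigator, so that the same rule applies at PBT and local centres.
- **Section 13.5:** state that only events assessed as related are counted as SARs.

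The cost is two form items, if the eCRF does not already hold them, and minor wording changes. No added visits or patient assessments are needed. It is best done early, since relatedness that was not recorded at the time would be hard to reconstruct after years of follow-up.

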#### 9.7 Follow-up assessments

Participants will be seen in the out-patient clinic after completion of PBT or photon RT for follow-up visits (post-end of PBT or photon RT) as follows: 1, 3, 6, 12, 24, 36, 48 and 60 months. Where relevant and possible, follow-up assessments should be performed during the closest chemotherapy pre-treatment assessment and within +/- 4 weeks of the scheduled follow up timepoint. Details of the follow-up assessments required at each of these follow-up time points are provided below.

Follow-up data will be collected at these time points by completing the relevant eCRF. At follow-up visits, data collected will include (but will not be limited to):

- Clinical assessment (clinical examination including CNS examination, documentation of concurrent medications of interest (including review of steroid use, anti-epileptics and hormonal therapies) and assessment of KPS)
- Clinician-recorded toxicities and CTCAE (until end of trial as per assessment schedule)
  - Pre-existing symptoms/side effects related to ODG or its treatment that predate APPROACH trial treatments should be recorded at the baseline assessment – these will not be considered as new toxicities
  - Pre-existing symptoms/side effects related to a non-ODG cause that pre-date APPROACH trial should be recorded at the baseline assessment – these will not be considered as new toxicities
- Neurocognitive function tests (see 9.10 Neurocognitive function tests)
- HRQoL questionnaires (EORTC QLQ-C30 and BN20, EQ-5D-5L, MFI, HADS, completed by participant))
- Endocrine assessment (see 9.11 Endocrine testing; not required at months 1 and 3)
- WPAI questionnaire and an additional health resource use questionnaire (completed by participant and primary caregiver)
- Caregiver Needs Screen questionnaire (completed by primary caregiver)
- MRI (not required at month 1)
- Documentation of clinical or radiological progression

Follow-up visits and assessments will continue until 60 months post-end of radiotherapy or until death, whichever is sooner.

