-  Participant must have confirmed that they are not pregnant with their doctor/treatment team within 7 days prior to each chemotherapy cycle (section 4.3.1 Pregnancy testing)
-  Required to assess response rates and progression-free survival and evaluated based on RANO criteria
-  MRI for radiotherapy planning to be done ideally within 21 days prior to the start of RT, but no more than 28 days of the CT simulation scan
-  CT simulation for RT to be done within 21 days prior to the start of RT
-  Including: EORTC QLQ-C30, EORTC BN20, EQ-5D-5L, Multi-dimensional Fatigue Inventory (MFI), Hospital and Anxiety Depression Scale (HADS)
-  Work & Productivity (WPAI) and Health Resource Use questionnaires will be assessed in participants and primary caregivers. The Health Resource Use will be collected at baseline and at annual follow-up only.
-  Caregiver Needs Screen to be completed by primary caregiver for each participant. Baseline data will also be collected at time of baseline questionnaire completion.
-  To be completed on any day the participant will receive one of their 5 final RT treatments
-  Endocrinopathy: Endocrine function will be assessed using blood tests. Dynamic/static testing will be performed for growth hormone/insulin-like growth factor-1 (GH/IGF-1), follicle-stimulating hormone/luteinizing hormone (FSH/LH)/ testosterone (males) & SHBG (males) /oestradiol (females), cortisol, thyroxine /tri-iodothyronine/ thyroid stimulating hormone (T4/T3/TSH) and prolactin. See section 9.11 Endocrine testing

 Participants may start PCV chemotherapy anywhere between 4 and 8 weeks post-end of RT. For each cycle of chemotherapy, a pre-treatment clinical assessment must be performed within 7 days prior to Day 1 of each cycle. Full blood count, urea and electrolytes, liver function tests, creatinine clearance and bilirubin should be performed within 7 days prior to the first chemotherapy cycle and within 3 days prior to each subsequent chemotherapy cycle  ARs and SARs should be monitored and reported, during trial treatment, up until the end of the trial

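### Non-fatal late harms that an unblinded site judges unrelated have no clear recording route, so late-toxicity counts by arm depend on attribution and may be incomplete

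*Protocol*

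**What the plan says.** **Definitions.** Section 10.1.4: "A Serious Adverse Reaction (SAR) is an SAE deemed to have been related to trial treatment". Section 10.1.2 sets the threshold for an adverse reaction: "This definition implies a reasonable possibility of a causal relationship which is supported by facts, evidence or arguments to suggest a causal relationship".

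**Recording rule.** Section 10.3.5 requires SARs and RUSAEs occurring during treatment to be entered "within 24 hours of the trial site team becoming aware of the event, regardless of causality". It continues: "Selected late toxicities occurring during follow-up must also be recorded and reported as above". No list follows and none is cited. The next paragraph of 10.3.5 has SARs and RUSAEs collected to the end of the trial.

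**Visit-level recording.** Section 9.7 lists, at each follow-up visit, "Clinician-recorded toxicities and CTCAE (until end of trial as per assessment schedule"), and sets aside only symptoms present before the trial. Footnote 15 to Table 3, attached to the CTCAE toxicity row for the same visits, says "ARs and SARs should be monitored and reported, during trial treatment, up until the end of the trial".

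**What is excluded.** Sections 10.1.1 and 10.2 say that non-serious events with no causal link to treatment are not collected. Neither says what happens to serious events judged unrelated.

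**Use of the data.** Section 11.2 defines the toxicity endpoint through adverse reactions, SARs and RUSAEs. Section 13.5 summarises these by arm for the acute and late periods, without a formal comparison.

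**The concern.** Section 1.3 places the main potential benefit of proton therapy in less normal-tissue damage and less long-term toxicity. Table B1 in Appendix B names stroke, second primary cancer, cataract and lasting visual or hearing damage among the very late radiotherapy harms, and includes seizures among the late effects of radionecrosis. All of these also occur in people who have never been irradiated. For one patient the cause is often uncertain, whereas comparing all occurrences between randomised arms does not need the cause to be settled.

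The plan counts such an event only if a clinician who knows the arm judges it related. An event left out at the visit is not in the trial database, and an analysis plan cannot restore it. The point therefore concerns what sites are told to collect, not what the SAP might later specify. At stake is the completeness of the late-harm table, which is also what the DMEC and later readers will use.

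**Working it through.** The core check is textual. The protocol gives no figure to reproduce.

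**Step 1. Follow a non-fatal late event through the text, by judged cause.**

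| Late, non-fatal event | What the protocol says | Result |
|---|---|---|
| Judged related, serious or not | 10.2 (radiotherapy reactions), Table 3 footnote 15, and 10.3.5 for SARs and RUSAEs: collected to the end of the trial | Recorded |
| Judged unrelated, non-serious (for example a cataract) | 10.1.1 and 10.2: not collected | Not recorded, by stated choice |
| Judged unrelated, serious (for example a stroke needing admission) | 10.1.3 defines an SAE, but 10.2 and 10.3 give reporting rules only for ARs, SARs and RUSAEs; the expedited forms in 9.20 include SAR and RUSAE forms but no SAE form | No clear route |

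**Step 2. Does the causality phrase in 10.3.5 fill the third row?** No, for two reasons. Its subject is SARs and RUSAEs, which 10.1.4 has already limited to related events, so the phrase either contradicts the definition or adds nothing to it. The sentence also covers events during treatment. Late events come under it only through the next sentence, on selected late toxicities, which names none.

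**Step 3. Does 9.7 fill it?** Not clearly. Section 9.7 states no attribution rule, so a site could record any new CTCAE event. The footnote on the matching Table 3 row speaks of ARs and SARs, which points the other way.

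**Step 4. What is unaffected?** Deaths are reported whatever the cause (9.14). Neurocognition (9.10) and endocrine function (9.11) are measured by scheduled tests. The primary analysis does not use these data.

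**Step 5. Scale, for illustration only.** The risks and recording shares below are assumptions, not estimates. Patients per arm: 123 randomised, or 0.70 × 123 = 86 after the 30% loss planned in 12.1. Events in both arms = 2 × risk × n. Events lost = events × (1 − share recorded).

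| Assumed combined 5-year risk | Events (n = 86 to 123 per arm) | Lost if 90% recorded | Lost if 70% | Lost if 50% |
|---|---|---|---|---|
| 4% | 6.9 to 9.8 | 0.7 to 1.0 | 2.1 to 3.0 | 3.4 to 4.9 |
| 8% | 13.8 to 19.7 | 1.4 to 2.0 | 4.1 to 5.9 | 6.9 to 9.8 |
| 12% | 20.6 to 29.5 | 2.1 to 3.0 | 6.2 to 8.9 | 10.3 to 14.8 |

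**Step 6. Would a difference in attribution between arms mislead?** Suppose an equal true risk of 8%, with 70% recorded on protons and 90% on photons. The table would show 0.08 × 0.70 = 5.6% against 0.08 × 0.90 = 7.2%, a gap of 1.6 points. The 95% half-width is 1.96 × √[(0.056 × 0.944 + 0.072 × 0.928)/n], which is 7.3 points at n = 86 and 6.1 points at n = 123. The gap lies well inside sampling error.

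**The case against.** The strongest reply is that the causality phrase is a timing rule: enter the event within 24 hours without waiting for attribution. Section 10.3.5 supports this, because it allows initial reports without a causality or expectedness assessment. This reading is fair. It also confirms that the phrase creates no route for unrelated late events.

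Second, the threshold in 10.1.2 is low, Table B1 already lists these harms as expected, and both arms receive cranial radiotherapy, so many such events will be attributed and recorded. This stands and limits the loss. It does not help with the events that a site does judge unrelated.

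Third, traces exist elsewhere. Section 9.12.3 collects hospital admissions and length of stay, MRI continues to 60 months, and unrelated non-serious events must be in the medical notes. These are partial sources and are not planned as event counts by arm.

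Fourth, collecting reactions rather than all events is a stated choice. That is so for non-serious events. The text makes no such statement for serious ones, and the proposal is a short list, not full adverse-event collection.

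A reader might infer more than the documents support:

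- **That late SARs are lost because only selected late toxicities are reported.** The next paragraph of 10.3.5, section 10.2 and footnote 15 all continue collection to the end of the trial.
- **That some sites will record unrelated strokes and others will not.** The text permits this but does not state it.
- **That the safety comparison favours protons.** Minimisation includes centre (7.6) and late follow-up is at the local centre in both arms (3.1.2), so differences between sites would mainly remove events from both arms. Whether attribution differs by arm, and in which direction, is unknown.
- **That relatedness is defined inconsistently or has no assessor.** Section 10.1.5 does word relatedness differently ("it resulted from administration of any research procedures"), and 10.3.5 names an assessor only for expectedness ("Assessment of expectedness must be made by an authorised medically qualified person"). The first is a definition attributed to the Health Research Authority and used for expedited reporting; the second may be settled on forms not shown. Neither carries the point.

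**Conclusion.** The point holds in a limited form. Non-fatal late events judged unrelated by an unblinded site have no clear recording route, and the wording of 10.3.5 does not provide one. The consequence is an incomplete, attribution-dependent count of rare late harms in a descriptive table. No hypothesis test, and neither the primary endpoint nor survival, is affected.

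The documents do not allow the size to be estimated, since they give neither event rates nor the share that sites would judge unrelated. Under the assumed ranges above, the loss runs from about 1 event to about 15 across both arms. In the unequal-recording example no between-arm conclusion would turn on it. The conclusion rests on the protocol text alone; the eCRF and the Trial Monitoring Plan are not shown and could narrow the gap. The change is worth making because it is cheap and because late normal-tissue harm is central to the reason for the trial.

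**What to change.** - **10.3.5, late events:** replace the unnamed selection with a list of at least non-fatal stroke, second primary cancer, new or worsening late seizures, cataract, and vision or hearing loss. Record every new occurrence in both arms at the existing visits to 60 months, whatever the judged cause, with relatedness as a separate item. State that the list is an exception to 10.2 and Table 3 footnote 15.
- **10.3.5, causality phrase:** delete it, or reword it as an instruction to report without waiting for the causality assessment, so that it agrees with 10.1.4.
- **13.5:** show all-cause counts by arm for the listed events beside the attributed counts.
- **Expedited reporting:** leave it limited to related events.

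The cost is a short list, one relatedness field if the eCRF lacks it, and wording changes. No visit or test is added. The downside is that some clearly unrelated events will be recorded.
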